##### **Pharmacy visit**

The patient visits the pharmacy once a week to collect the medication in a weekly dosing aid. The pharmacist provides the patient with information about the medication (especially at the beginning of the intervention and if a new medication is prescribed) and motivates the patient to take the medication, to self-manage symptoms and weight changes (e.g. daily weighing, weight diary).

During these weekly visits, the pharmacist inquires after potential side effects, medication adherence, as well as signs and symptoms of a potential cardiac decompensation (e.g. shortness of breath). The pharmacist measures blood pressure and pulse (SOP BAK, see 9.1). If significant changes in vital signs are detected or if the patient reports relevant symptoms or signs (e.g. a significant weight increase), the pharmacist contacts the physician or recommends the patient to contact his physician.

If the patient does not collect his medication, the pharmacy contacts first the patient or his caregiver(s). Additionally, in case of difficulties, the pharmacy contacts the medical practice.

##### **Adoption of the intervention**

a) Once the patient has attended the weekly visits in the pharmacy for a minimum of four continuous weeks and if needed, the patient and his pharmacist can agree on bi-weekly visits to the pharmacy.

b) When a patient cannot visit the pharmacy, e.g. the patient is ill/home-bound, the pharmacy can either deliver the weekly dosing aid to the patient's home or it can be dispensed to a caregiver. If the patient is absent for longer than a week, e.g. on holiday, the pharmacy can supply the patient with more than one weekly dosing aid. As the pharmacy visit is an essential part of the intervention, it is important, that the patient attends the interview at the pharmacy regularly. Hence, the supply of weekly dosing aids for more than two weeks should be strictly limited to these exceptions.

## 9 Training and Monitoring

### 9.1 Training and Information Material

Training will be performed by ABDA, UdS and IZKS Mainz. Participating pharmacists and physicians are trained either by telephone, on site or during a workshop about study-specific aspects and will receive information material. They receive standardized material including study guidelines, checklists and forms, the study protocol, study material, information about the electronic case report form (eCRF), and a contact list.

A telephone hotline to UdS as well as a website ([www.pharm-chf.de](http://www.pharm-chf.de)) is available as information source and for requests of participating pharmacists and physicians. When necessary, questions will be forwarded to ABDA or IZKS Mainz.

Medication is dose-dispensed based on the recommendations of the BAK, i.e. by dual control. A SOP of the BAK for the measurement of blood pressure and pulse is available in the intervention pharmacies.

### 9.2 Monitoring

Monitoring visits are conducted by the IZKS in the medical practices. As described in the study specific monitoring manual, monitoring will be done either by personal visits of a clinical monitor or by telephone contacts according to SOP of the IZKS Mainz (if applicable). The monitor checks the informed consent forms and reviews the entries into the eCRF based on source documents. The physician allows the monitor access to all essential documents and provides support to the monitor.

The IZKS Mainz assists the physician to conduct the study according to the protocol as well as regulatory and ethical requirements.

Moreover, pharmacists are assisted to conduct the study according to the protocol by employees (research associates) of ABDA.

## 10 Data Management

### 10.1 Responsibilities

On behalf of the sponsor, IZKS Mainz conducts the data management of the PHARM-CHF study. A detailed methodology for the data management in this study will be documented in a data management plan. The document may modify the procedures outlined in this protocol. However, any major modifications of the data handling will also lead to a protocol amendment.

### 10.2 Data Collection

Obtained data is documented in an electronic case report form (eCRF), with an exception of the patient questionnaires. Patients answer questionnaires using a paper form. All protocol-required information collected during the study is entered by the investigator, or a designated representative in the eCRF. The paper-based data is entered by the IZKS Mainz into the study database. The investigator and the study site staff will receive system documentation, training and support for the use of the eCRF. In case of new study site staff, the training can be performed by personnel at the study site. IZKS Mainz can be contacted to support the data entry.

All data changes (entry, modification and deletion) are recorded automatically in an electronic audit trail by storing the individual subject, the original value, the new value and time and date of the change. Previous data can be viewed or restored by the audit trail. All electronic data is entered by the site in compliance with applicable record retention regulations.

The system is secured to prevent unauthorized access to the data or the system. Only people provided with a user ID and a password are able to enter or change data. The investigator maintains a list of individuals who are authorized to enter data.

Computer hardware and software (for accessing the eCRF data) will be maintained at the site. The remote data entry (RDE) system is capable to make exact copies of data in legible paper form for audits. The architecture of the computer system of the IZKS Mainz will be described in the data management plan.

### 10.2.1 Additional Sources for Data Collection

To complete the data obtained from pharmacies and medical practices, there are also other sources to obtain information e.g., about events. Health insurance funds (Statutory Health insurance (SHI) and private) are asked for information, as well as German data processing centres (*Apothekenrechenzentren*) and comparable resources, e.g. registration offices (*Einwohnermeldeämter*) or health offices. All data will be kept in safe and confidential custody at IZKS Mainz.

### 10.2.2 Assessment of Safety

In case of hospitalizations, the blinded documents are sent to the clinical event committee (CEC) for adjudication according to pre-specified criteria in the CEC charter. Adjudicated events will be categorized by their cause and assigned into cardiovascular and non-cardiovascular events.

## 10.3 Data Handling

During data entry, integrity checks help to minimize entry failures. These data entry checks are defined in the data validation plan. The data entry system allows the study monitors to control the entry process with the help of the system-own review functions. Comments and requests can be processed by the study site just in time.

During the study, data is exported into the statistical analysis system (SAS) and checked additionally for plausibility, consistency and completeness. Based on these checks, queries are produced. Any missing data or inconsistencies are reported back to the respective site and clarified by the responsible investigator. If all corrections are done, the database is closed and used for statistical analyses.

All collected data will be processed according to the German Data Protection Law and handled in strictest confidence. To cover all relevant aspects of data protection a data protection commissioner is involved. A Data-Safety concept will be implemented and specified in a separate document. The latter will be prepared in cooperation with and handed in for approval to the data protection commissioner. Personal data will be strictly separated from the study database.

## 10.4 Storage and Archiving of Data

The investigator archives all study data (e.g. subject identification list, informed consent) and relevant correspondence in a standardized project folder. This folder, all source data and all documents are archived after finalization of the study according to the legal regulations.

IZKS Mainz assures storage and archiving of the electronic data during the study. After completion of the study all electronic data is handed over to the sponsor.

## 11 Biometrics

### 11.1 Sample Size

[figure not shown]

Figure 2: Sample Size Calculation

The primary efficacy variable is adherence to CHF medication. We conservatively assume an improvement of the summary PDC  $\geq 10\%$  in the intervention group compared to usual care as clinically relevant.

Assuming a mean PDC in the year before randomization of approximately 0.7 a sample size of  $N=176$  patients (88/group) is needed to detect a 10% (SD 22%) improvement between the intervention group and the usual care group with a power of 85% and an alpha of 5%. Assuming a dropout and lost to follow up of 30%  $N=248$  patients have to be enrolled in the study.

The study is powered for the primary efficacy variable only.

### 11.2 Interim Analysis

No interim analysis will be performed.

### 11.3 Analysis Populations

#### Intention to treat

The intention to treat (ITT) population consists of all patients who have post-baseline data available and who did not fail to satisfy major entry criteria. Patients in the intervention arm (with or without withdrawal of consent), for whom no consolidated medication plan is available i.e., subjects failed to comply with

the study protocol at entry (i.e. did not undertake the medication review at the pharmacy - which is comparable of not taken any trial medication), have no post-baseline data available.

### **Per Protocol**

The per protocol (PP) population consists of all subjects of the ITT population who completed the study without major protocol violations. These are violation of inclusion criteria, meeting exclusion criteria, post-baseline data not available, consolidated medication plan not available (intervention group patients only) and premature termination (except death). As data for patients withdrawn (with withdrawal of consent) from the study will be anonymized immediately, pseudonymized data acquisition from other sources e.g., health insurance funds is impossible.

## **11.4 Statistical Methods**

The main analysis comprises the eCRF data and pharmacy claims data of prescribed medicinal products dispensed at community pharmacies from data processing centres (*Apothekenrechenzentren*) and health insurance funds (statutory and private) and hospitalization data from health insurance funds. On behalf of the sponsor, IZKS Mainz conducts the main analysis of the PHARM-CHF study. The PDC will be determined at the PMV (University Cologne) and will be submitted to the IZKS Mainz for further analysis. Analyses regarding the intervention in participating pharmacies like analyses of drug-related problems (DRPs) and medication discrepancies are based on the eCRF and data documented during the intervention from pharmacists. These analyses will be performed by the Department of Medicine, ABDA, Berlin. The detailed methodology for the statistical analysis of this study will be documented in a statistical analysis plan (SAP). The SAP has to be signed by the scientific heads of the study, the statistician at IZKS and the study coordinator at ABDA.

### **11.4.1 Primary Efficacy Analysis**

The primary efficacy analysis is the analysis of the PDC for three CHF medications (ACEi/ARB, BB and MRA). The pharmacy claims data are provided by data processing centres and health insurance funds. If health insurance data are not available for all patients, an analysis will be performed comparing the data from health insurance funds and data processing centres. The analysis will be adjusted for data from health insurance funds (yes/no).

The PDC will be analysed by a two-sided stratified Wilcoxon signed-rank test (van Elteren test) on a two-sided level of significance of 5%.

The following hypothesis will be tested:

$H_0: m_i = m_c$  vs.  $H_1: m_i \neq m_c$ ,

Where  $m_i$  denotes the median value of the intervention group and  $m_c$  denotes the median value of the control group.

Although statistical guidelines ("Points to consider on adjustment for baseline covariates") suggest adjusting the analysis for all stratification variables of the randomization process, this is omitted. It is desired to get a robust result, if one treatment regimen is favourable to the other across all stratification factors. Nevertheless, supportive analyses adjusting for the stratification factors will be conducted as sensitivity analyses.

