STUDY POPULATION	
Inclusion Criteria
 
 
- Age: 60 years and older
 
- Diagnosis of chronic heart failure (CHF)
 
- Stable CHF medication including a diuretic
 
- Hospitalization for decompensated heart failure within past 12 months OR a value of <math>\geq 350</math> pg/mL for BNP or <math>\geq 1400</math> pg/mL for NT-proBNP
 
- Written informed consent
 

	
Exclusion Criteria
 
 
- Regular/assisted use of a weekly dosing aid
 
- Unwillingness or inability to visit a participating pharmacy once a week
 
- Planned cardiac surgery
 
- Life-expectancy < 6 months
 
- Unwillingness or inability to comply with the study protocol (including drug abuse or alcohol dependency)
 
- Participation in other studies (currently or in the last 4 weeks)
 

DURATION OF THE STUDY	The mean follow-up is expected to 24 months with a minimum of 12 months.
NUMBER OF SUBJECTS	
N = 248
 
 
- Estimated effect of intervention: 10% (SD 22%)
 
- <math>\alpha = 0.05</math>, power: 85%
 
- Calculated sample size: 176 + 30% drop out
 

STUDY SITES	
Approximately 40 medical practices
 
Approximately 80 pharmacies

STUDY VISITS	
Intervention and control group:
 
 
- Visits in the medical practice at baseline (V1), after 12 months (V3), and at the end of the study (V6), and, if applicable, after 24 months (V5)
 
- Telephone visits by the medical practice after 6 months (V2) and, if applicable, after 18 months (V4)
 

INTERVENTION	
Regular, pharmacy based intervention conducted in cooperation with the treating physician:
 
 
- Medication review (Type 2a) at baseline: Recording of all medicines currently taken (prescribed medication and self-medication), check for drug-related problems, consolidation of a medication plan considering medication list of treating physician
 
- Regularly (weekly or bi-weekly): Dose-dispensing of the medication (weekly dosing aid), discussion and counselling regarding medication, adherence, potential side effects, and signs and symptoms of cardiac decompensation, blood pressure and pulse measurement, updating medication plan if necessary
 
- If required: Contact with patients' physician
 

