### 11.4.6 Randomization

Eligible patients are assigned in a 1:1 ratio to the intervention or control group. Minimization with 20% residual randomness is used to ensure balance of the following characteristics: Gender (male/female), age (<75, ≥75), NYHA functional class (I and II, III and IV), PHQ-9 (score <10, ≥10), diabetes mellitus (yes/no), study region (according to regional Associations of Statutory Health Insurance Physicians (KV-Region)).

A web-based randomization tool developed by IZKS Mainz is used within this study allowing investigators to randomize patients via a secure web interface.

Subjects withdrawn from the study retain their identification codes (i.e. patient number). New subjects must always be allotted a new identification code.

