1.2 Sample size considerations

Assuming a baseline PDC for cardiovascular medication of 0.7 and a standard deviation of the PDC of 0.22 a sample size of N=176 (88/group) patients is needed to detect a 10% difference between the intervention group and the usual care group with a power of 85% and an alpha of 5%. Assuming a dropout and lost to follow-up of 30% N=248 patients have to be enrolled in the study. The planning is based on a two-sided t-test and performed by means of SAS Version 9.4.

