The primary analysis population for both adjustment types is the ITT population. However, the primary analysis (both adjustments) will be repeated for the PP population for sensitivity. As a further sensitivity analysis an analysis of (co)variance (AN(C)OVA) for the PDC will be done with PDC as dependent variable, and the further fixed effects treatment (intervention vs. control), data from health insurance funds (yes/no), sex (male vs. female), age (≤ 75 vs. > 75 years), NYHA functional class (I and II vs. III and IV), PHQ-9 score (score < 10 vs. ≥ 10) and diabetes mellitus (yes vs. no). The study region will be omitted since this may lead to an over determination of the analysis model.

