7.10.2 Secondary safety analyses

All-cause mortality or unplanned cardiovascular hospitalizations as recurrent event

All-cause mortality or unplanned cardiovascular hospitalizations will be analysed by Negative Binomial Regression with treatment as factor and data from health insurance funds (yes/no) and time within study as offset variable. The logarithm will be used as link function.

Events regarding hospitalization are recorded in the medical practices (eCRF) and will be provided by health insurance funds. However, health insurance data were not available for all patients included in the study. Differences between patients with and without data from health insurance funds cannot be excluded. Therefore, the analysis will be adjusted for data from health insurance funds (yes/no).

The following SAS code can be used:

```
PROC GENMOD DATA=indata;  
    CLASS treatment;  
    MODEL primsafetyendpoint = treatment ... / LINK=log DIST=negbin  
    OFFSET=log_time  
    LSMEANS treatment / DIFF CL;  
RUN;
```

The results are provided showing parameter estimates, LSMEANS and LSMEAN-differences together with their corresponding p-values and 95% confidence intervals as well as the negative binomial dispersion parameter.

Additionally, the number of deaths and unplanned cardiovascular hospitalizations will be analysed descriptively.

Although statistical guidelines (“Points to consider on adjustment for baseline covariates”) suggest adjusting the primary analysis for all stratification variables of the randomization process, this is omitted. It is desired to get a robust result, if one treatment regimen is favourable to the other across all stratification factors.

Several analyses for sensitivity are performed.

1. The analysis is repeated for the PP population
2. The analysis is repeated, but the characteristics from the randomization process are also included in the analysis model (sex (male vs. female), age (<75 vs. ≥75 years), NYHA functional class (I and II vs. III and IV), PHQ-9 score (score <10 vs. ≥10), diabetes mellitus (yes vs. no). All characteristics are included in the model as covariates at the same time without any interaction terms.
3. There is a Kaplan-Meier analysis for the time to first event (death or unplanned cardiovascular hospitalization, whatever occurs first). If no event is reported, time will be censored at the time of last contact. The median time to event will be displayed together with the 25% and the 75% quartile.

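### Neither primary efficacy analysis includes the factors used to minimise allocation, so some efficiency is lost to the extent that those factors predict PDC

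*Protocol*

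**What the plan says.** Protocol 11.4.6 states: "Minimization with 20% residual randomness is used to ensure balance of the following characteristics". It then lists gender, age, NYHA class, PHQ-9, diabetes and KV region. SAP 1.4 repeats the list.

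Protocol 11.4.1 makes a two-sided van Elteren test at 5% the primary efficacy analysis, stratified by whether health insurance data are available. That stratum is not a minimisation factor. The section acknowledges the guideline that recommends adjusting for the stratification variables, declines to follow it, and explains: "It is desired to get a robust result, if one treatment regimen is favourable to the other across all stratification factors". Adjusted analyses are kept as supportive.

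SAP 7.8 runs the primary analysis twice in the ITT population. One run is the van Elteren test. The other is an ANCOVA for insurance data and baseline adherence. Each is tested at an undivided 5%, and neither contains a minimisation factor. Five of the six factors appear only afterwards: "As a further sensitivity analysis an analysis of (co)variance (AN(C)OVA) for the PDC will be done with PDC as dependent variable". That model adds sex, age, NYHA class, PHQ-9 and diabetes and leaves region out.

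SAP 7.10.2 gives the same argument for the composite recurrent-event model, saying that guidelines "suggest adjusting the primary analysis for all stratification variables of the randomization process, this is omitted". It then lists a repeat of that model with the five factors as a sensitivity analysis.

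**The concern.** Minimisation removes most of the chance difference between arms in the listed factors. An analysis that ignores them still counts the outcome variation they cause as noise. If the factors predict PDC, the standard error is larger than the design warrants, the actual type I error falls below the nominal 5%, and power is given away.

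The stated reason does not support the omission. A main-effects adjustment still yields one overall treatment effect. Whether the effect is consistent across the factors is answered by the interaction analyses already planned in Protocol 11.4.5 and SAP 7.11. Rank-based robustness need not be given up either: the SAP's own code uses modified ridit scores, and these can be analysed with covariates.

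**Working it through.** **Plan's own figure.** SAP 1.2 gives the basis: "Assuming a baseline PDC for cardiovascular medication of 0.7 and a standard deviation of the PDC of 0.22", a difference of 10 percentage points, 85% power and 5% alpha. It adds: "The planning is based on a two-sided t-test and performed by means of SAS Version 9.4". A two-sample t-test with these inputs needs 87.88 per group, so 88 per group and 176 in total, with power 85.05%. The stated 176 reproduces.

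**Inputs not in the documents.** R² is the share of PDC variance explained by the five factors in the SAP's sensitivity model. No document gives it, so 0 to 0.15 is assumed.

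**Formulas.** These are normal approximations for a mean difference, with perfect balance on the factors, k = √(1 − R²), and d = difference / unadjusted standard error:

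- actual size of the unadjusted test = 2 × [1 − Φ(1.96 / k)]
- unadjusted power = Φ((d − 1.96) / k)
- adjusted power = Φ(d / k − 1.96)

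For the planned design, d = 1.960 + 1.036 = 2.996. For the ITT population in SAP Table 2 (110 and 127), the standard error is 0.22 × √(1/110 + 1/127) = 0.02865, so d = 0.10 / 0.02865 = 3.490.

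| R² (assumed) | Actual size, unadjusted | Planned N: unadjusted / adjusted power | Gain | ITT 110/127: unadjusted / adjusted power | Gain |
|---|---|---|---|---|---|
| 0 | 5.00% | 85.00 / 85.00% | 0 | 93.70 / 93.70% | 0 |
| 0.05 | 4.43% | 85.62 / 86.74% | 1.12 | 94.17 / 94.74% | 0.57 |
| 0.10 | 3.88% | 86.27 / 88.46% | 2.19 | 94.66 / 95.72% | 1.06 |
| 0.15 | 3.35% | 86.95 / 90.15% | 3.20 | 95.15 / 96.60% | 1.45 |

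At 88 per group and R² = 0.10, the standard error falls from 0.0332 to 0.0315.

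**Check by simulation.** Real balance is not perfect, so minimisation itself was simulated, with 2,000 runs per setting and a Monte Carlo error of about 0.5 points near 5%. The settings were 258 randomised patients, with 20 intervention patients and 1 control removed at random. The van Elteren test was compared with an ANCOVA on the five factors plus insurance status.

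| R² | Size, van Elteren / ANCOVA | Power, van Elteren / ANCOVA |
|---|---|---|
| 0 | 5.35 / 5.45% | 93.5 / 94.1% |
| 0.05 | 4.15 / 4.20% | 92.35 / 93.6% |
| 0.10 | 3.80 / 4.95% | 92.35 / 95.65% |
| 0.20 | 3.05 / 4.55% | 94.25 / 97.55% |

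With 176 patients and no exclusions, the van Elteren size was 5.25% at R² 0.05, 4.95% at 0.10 and 2.65% at 0.20. Conservatism is therefore clear only for the larger R². Part of the power gap is the difference between a rank test and a linear model on normal data: at R² = 0 and 176 patients, power was already 81.7% against 84.15%.

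The simulation also assumed factor prevalences of 50, 50, 50, 25 and 40%, nine equal regions, insurance data for half the patients, the preferred arm given with probability 0.8, and normally distributed PDC.

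**The case against.** The omission is a disclosed choice. The protocol names the guideline, states the departure and pre-specifies the adjusted analyses, so readers will see both results. A size below 5% harms nobody's confidence in a positive finding. On the formulas above, unadjusted power never drops below the planned 85%, and at the ITT size it is about 94% or more. The second primary analysis already adjusts for baseline adherence. All of this stands, and it limits the weight of the point. It does not answer why the factors used for allocation are missing from both primary analyses, since the only reason given does not bear on the matter.

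Three stronger readings are tempting, and the documents do not support them.

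- A reader might infer that the primary test is invalid. It is not: ignoring balanced prognostic factors makes it conservative, not anti-conservative.
- A reader might infer that the whole primary conclusion is conservative. That description fits a single test only. SAP 7.8 runs two primary analyses at an undivided 5% each.
- A reader might infer that adjustment would repair the unequal ITT exclusions in SAP Table 2 (20 intervention patients against 1 control). Seventeen of the 20 were removed for having no medication review or consolidated plan, a reason that removed no controls. That is selection after randomisation. Five baseline factors can correct a measured imbalance in themselves but cannot remove that selection.

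**Conclusion.** The point holds as a modest, conditional loss of efficiency. If the five factors explain 5 to 15% of PDC variance, the unadjusted test has an actual size of about 4.4% to 3.4% under near-perfect balance. Adjustment would then gain about 1 to 3 power points at the planned 176 patients, or about 0.5 to 1.5 at 110 and 127. If the factors do not predict PDC, nothing is lost.

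These figures rest on the assumed R², normal approximations, the planning SD of 0.22 and a true difference of 0.10. Residual randomness and the exclusions weaken the balance and so shrink the conservatism. The change is worth making because the covariates are already in hand, not because the result would otherwise be unsound.

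**What to change.** Amend Protocol 11.4.1 and SAP 7.8 together, before outcomes by treatment group are seen. Changing the SAP alone would leave the two documents in conflict.

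1. Reconcile the age cut-off to the one the minimisation actually used. Protocol 11.4.5 and 11.4.6 and SAP 7.10.2 have <75 / ≥75. SAP 1.4, 5.3, 7.8 and 7.11 have ≤75 / >75.
2. Name one covariate-adjusted analysis as primary. A suitable choice is rank ANCOVA: modified ridit scores of PDC within insurance strata, in a linear model with treatment, sex, age group, NYHA class, PHQ-9 and diabetes. Add the 183-day baseline PDC where available, and say how patients without it are kept, because SAP 6.1 allows no substitution. Promoting the AN(C)OVA already in SAP 7.8 is simpler, but it makes a parametric model primary for an outcome bounded by 0 and 1 and replaces the hypothesis on medians.
3. Keep the unadjusted van Elteren test as a sensitivity analysis.
4. State the status of the existing ANCOVA with baseline adherence, so that a single test carries the 5%.

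Region may stay out, as now. Reordering the models in SAP 7.10.2 is optional, since their p-values are exploratory.

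The cost is a protocol amendment, a SAP revision and some programming, because rank ANCOVA is not in the current plan. No new data are needed: minimisation requires the five factors at randomisation, and the SAP already requests baseline claims data.
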